We will also frequently assess participant treatment reactions with established varenicline symptom checklists and validated suicidality and depression scales. These assessments will be conducted at each visit before, during, and after the treatment phase. Also, given recent reports indicating the potential risk for adverse cardiovascular effects from varenicline (Singh et al., 2011 and www.fda.gov/Drugs/DrugSafety/ucm259161.htm), blood pressure will be assessed at each in-person visit to monitor cardiovascular reactions to study medication.

We will use an established coding and reporting system for side effects used in our ongoing multi-site varenicline trial (U01 DA020830). In this system, study personnel are trained by physicians and psychologists to administer established side effects measures, including validated scales of depression and suicidality. If a side effect report or a score on an established scale indicates a safety concern, site PIs and physicians/psychologists are immediately notified and will determine a course of action (e.g., continue to monitor, stop medication). Participants are given contact information so that, if an adverse event occurs, they can contact study physicians 24-hours a day. These side effects are also coded and managed by PIs and site physicians/psychologists. All serious adverse events are reported to the IRB, NIH, FDA, and Pfizer in accordance with data safety and monitoring reporting procedures, and they may also be referred to an out-patient department at PENN/NU or to the ER. Lastly, a study-specific Data Safety and Monitoring Board will be convened for this trial to monitor side effects.

Outcome Assessments.

The primary outcome variable is 7-day point prevalence abstinence at Weeks 24 and 52, confirmed with CO (Hughes et al., 2003). All participants will be asked to attend the center at Weeks 24 and 52 and CO will be collected for all participants to avoid potential bias. Other outcomes include: 7-day point-prevalence abstinence (CO-verified) at Week 12 and 26, smoking rate, prolonged abstinence to Weeks 12, 24, 26, and 52 (relapse defined as 7 consecutive days of self-reported smoking, after a 2-week grace period), continuous abstinence at Week 12, 24, 26, and 52 (no smoking between the quit day and the follow-up measure), time to 7-day relapse (no grace period), lapse and recovery events, and QOL.

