Note: If a participant is unable to complete a session in-person, assessments and counseling may be completed over the telephone. Every attempt will be made to accommodate participants' schedules & reduce the likelihood of missed sessions. Missed sessions will not be submitted as protocol deviations.

Table 2: Study Measures/Events

| Study Week | -1 | 0 | 1 | 4 | 8 | 12 | 14 | 18 | 24 | 26 | 52 |
|--|-----------|----------------|----------------|----------------|----------------|----------------|----------------|----------------|----------------|----------------|----------------|
| Session Name | Intake | Pre-Quit | TQD | W4 | W8 | W12 | W14 | W18 | W24 | W26 | W52 |
| Session Type | In Person | In Person | In Person | In Person | Phone | In Person | Phone | Phone | In Person | Phone | In Person |
| TREATMENT | | | | | | | | | | | |
| Standard Varenicline | | X | X | X | X | X | | | | | |
| Extended Varenicline | | X | X | X | X | X | X | X | X | | |
| Counseling | | X | X | X | X | X | X | X | | | |
| SCREENING/COVARIATES | | | | | | | | | | | |
| Urine Pregnancy Screen | X | | | | | | | | | | |
| Breath Alcohol Concentration | X | | | | | | | | | | |
| Blood Pressure | X | X | X | X | | X | | | X | | X |
| Psychiatric History (MINI) | X | X ^a |
| Medical History | X | | | | | | | | | | |
| Concomitant Medications | X | X | X | X | X | X | X | X | X | X | X |
| Demographics | X | | | | | | | | | | |
| Smoking History/FTND | X | | | | | | | | | | |
| ETOH History | X | | | | | | | | | | |
| Depression/Anxiety (HADS) | X | X | X | X | X | X | X | X | X | X | X |
| Lifetime MDE ([name] et al., 2011) | X | | | | | | | | | | |
| MEDIATORS | | | | | | | | | | | |
| Withdrawal Symptoms (SJWF) | | X | X | X | | X | X | | X | X | |
| Smoking Urges (QSU-B) | | X | X | X | | X | X | | X | X | |
| Affect (PANAS) | | X | X | X | | X | X | | X | X | |
| Cognitive Function (FACT-2) | | X | X | X | | X | X | | X | X | |
| Cigarette Evaluation Scale (CES) ^c | | X | X | X | X | X | X | X | X | | |
| Cue-elicited smoking urges (Choice Performance Task) | | X | X | X | | X | | | X | | X |
| Pearlin Mastery Scale (PMS) | X | | X | X | | | | | | | |
| TREATMENT VARIABLES | | | | | | | | | | | |
| Adherence (Pill Count) | | | X | X | X | X | X | X | X | X | |
| Adherence (Blood) | | | | X ^b | | | | | | | |
| Side Effects Checklist (SEC) | | X | X | X | X | X | X | X | X | X | X |
| Side Effects (Open-Ended) | | | X | X | X | X | X | X | X | X | X |

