| Suicidality (CSSRS) | X | X | X | X | X | X | X | X | X | X | X |
| Integrity of the Blind | | | | | | | X | | | X | |
| Program Satisfaction | | | | | | X | | | X | | |
| OUTCOMES | | | | | | | | | | | |
| Smoking Rate (TLFB) | | X | X | X | X | X | X | X | X | X | X |
| Carbon Monoxide (CO) Test | X | X | X | X | | X | | | X | | X |
| Quality of Life (SF-12) | | X | X | X | X | X | X | X | X | X | X |

*TQD = Target Quit Day *W= Week

*Note: Target Quit Day visit may occur +3 days from target date; Week 4, 8, 12, 14, 18, 24, and 26 visits may occur +/- 1 week from target date. The Week 52 visit may occur +/- 2 weeks from target date. Window extensions are subject to PI approval.

^a Administered only if HADS score exceeds borderline score for either anxiety or depression.

^b Only completed in 50% of participants enrolled at Penn. Will not be administered if participant has discontinued study medication for 14 or more consecutive days prior to scheduled session.

^c Administered only if participant has smoked a cigarette in the past 24 hours.

Screening/Covariate Measures.

Urine Pregnancy Screen

The urine pregnancy screen will assess for current pregnancy in all women and will be administered at the Intake Session.

Breath Alcohol Concentration/ETOH History

The breath alcohol concentration (BrAC) assessment will be administered at the Intake Session. The breath alcohol monitor assesses expired breath for alcohol content. Any reading >0.000 indicates alcohol consumption within the last 14 hours. The ETOH history form will be administered at the Intake Session visit and will ask subjects about their alcohol consumption over the past seven days.

Blood Pressure

Participants presenting at Intake with a blood pressure reading above 160 mmHg systolic and/or 100 mmHg diastolic will be ineligible for the study. Participants presenting at Intake with an elevated blood pressure reading between 150-160 mmHg systolic and/or 90-100 mmHg diastolic will have a second blood pressure reading taken after a ten minute period in which the participants will be instructed to sit comfortably. If, after the second reading:

- A participant has a blood pressure between 150-160 mmHg systolic and/or between 90-100 mmHg diastolic, the study physician will evaluate his/her situation and the participant may be withdrawn from the study.
- A participant has a blood pressure reading above 160 mmHg systolic and/or 100 mmHg diastolic, s/he will be ineligible for the study.

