Smoking status is assessed using the timeline follow-back method (Brown et al., 1998) as done previously (Lerman et al., 2004; [name] et al., 2010b) and by using breath CO to verify self-report. Participants are considered abstinent if they self-report abstinence (not even a puff of a cigarette) for >7 days prior to the Week 24 and 52 assessment and have a breath CO of <10ppm at the time-point (SRNT, 2002; Hughes et al., 2003). As per convention, participants are assumed to be smoking if they self-report to be smoking at the time-point, cannot be reached to provide data at the time-point, fail to provide a breath sample at the time-point, or provide a breath sample at the time-point that is >10ppm (SRNT, 2002).

Cessation/Smoking Rate: Daily smoking (presence and rate) will be assessed at each visit after Intake Session with the well validated timeline followback method (TLFB). These data can be used to assess

the timing and rates of lapses (smoking episodes not lasting 7 days), recovery events (return to abstinence), and relapse events, as well as to monitor changes in smoking rates (i.e., # cigarettes/day). These data will also be used to compute and assess secondary measures of smoking cessation (e.g., continuous and prolonged abstinence).

Carbon Monoxide (CO) Test: Carbon monoxide will be measured at each in-person visit to confirm smoking status.

Other Smoking Measures (secondary)

As per recommendations (Hughes et al., 2003), we will also assess: prolonged abstinence to Weeks 12, 24, and 52 (relapse is 7 consecutive days of self-reported smoking, after a 2-week grace period), continuous abstinence at Weeks 12, 24, and 52 (no smoking between the quit day and follow-up), time to 7-day relapse (no grace period), smoking rate, and lapse (smoking episodes < 7 days) and recovery (return to 24-hour abstinence) events.

Quality of Life (QOL)

The Short-Form Health Survey (SF-12) will assess QOL (Ware et al., 1996). This scale yields physical and mental subscales, has been used to assess cancer patient QOL (McCorkle et al., 2009), has demonstrated validity and reliability (Gandek et al., 1998), and has been used in smoking cessation trials with cancer patients ([name] et al., 2010a). The SF-12 will be administered at all visits following the Intake Session.

2. Statistical Analysis

Power

Power is provided for the primary aims since the exploratory aim is hypothesis generating. All comparisons are 2-sided.

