Aim 1: Compare standard varenicline treatment (12-weeks active then 12-weeks placebo) to extended varenicline treatment (24-weeks active) for treating nicotine dependence among cancer patients. The hypothesized effect of treatment arm (i.e., the difference in quit rates between subjects receiving standard or extended treatment) will be tested by a treatment arm term in a binomial family with logit link (logistic regression) model that possibly includes terms for covariates. Outcomes of the logistic regression analyses will be characterized by odds ratios (e.g., odds of quitting smoking) and 95% confidence intervals. Although quit-rates at the end of 24 and 52 weeks will represent our primary outcome variables, similar logistic regression analyses will be performed for other assessments of quit rates (e.g., quit rates at Weeks 12 and 26). This model will be used for measures of prolonged and continuous abstinence as well. In addition, as many participants will fail to become completely abstinent, the negative binomial family log link for count data will be used to examine the main effects of treatment arm on changes in smoking rate. Time to (recurrent) event models will be fitted using Cox regression, stratified by event sequence, as in [name] et al. (2010).

Aim 2: Assess effects of extended varenicline therapy on QOL and varenicline side effects. Repeated-measures MANOVA will examine differences across treatment arms in mental and physical QOL over the trial. Covariates will be included, such as medical treatment history. We will compare treatment arms in terms of the frequency of severe side effects (individual and total). Logistic regression will test against the lower boundary on percent reporting only mild-moderate (i.e., < severe) side effects. The hypothesis test for equivalence is whether the OR is out of the prescribed range for the difference between the treatment arms.

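### Week 26 point-prevalence abstinence is listed as CO-verified, but Week 26 is a phone session with no CO test scheduled, so the outcome cannot be measured as defined.

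*Combined protocol and SAP*

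**What the plan says.** All references are to the combined protocol and SAP.

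- **Outcome Assessments** (Study Procedures) names CO-confirmed 7-day point prevalence abstinence at Weeks 24 and 52 as primary. Among the other outcomes it lists "7-day point-prevalence abstinence (CO-verified) at Week 12 and 26". It promises attendance and testing for everyone only at the primary weeks: "All participants will be asked to attend the center at Weeks 24 and 52 and CO will be collected for all participants".
- **Table 2, session-type row**, from Week 12 onward (Weeks 12, 14, 18, 24, 26, 52), reads "In Person | Phone | Phone | In Person | Phone | In Person". Week 26 is a phone session.
- **Table 2, CO row**, over Weeks -1, 0, 1, 4, 8, 12, 14, 18, 24, 26 and 52, reads "Carbon Monoxide (CO) Test | X | X | X | X | | X | | | X | | X". The Week 26 cell is empty.
- **Outcomes Variables, Carbon Monoxide (CO) Test**: "Carbon monoxide will be measured at each in-person visit to confirm smoking status".
- **Outcomes Variables, Abstinence (primary)** requires self-reported abstinence "prior to the Week 24 and 52 assessment and have a breath CO of <10ppm at the time-point". It counts as smoking, among others, those who "fail to provide a breath sample at the time-point".
- **Statistical Analysis, Data Analysis, Aim 1**: "similar logistic regression analyses will be performed for other assessments of quit rates (e.g., quit rates at Weeks 12 and 26"). No CO qualifier appears there.

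**The concern.** An outcome defined by a breath test is placed at a session where no breath test is scheduled. The plan does not say what replaces the test at Week 26, so whoever runs the analysis must choose.

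Carrying over the breath-sample rule from the primary outcome yields no information. Using self-report yields an estimate, but one that would sit under a CO-verified label beside Weeks 12, 24 and 52, where CO is scheduled. A reader comparing Week 24 with Week 26 could not separate a change in abstinence from a change in how abstinence was measured. Extended-arm treatment ends on Day 168, so Week 26 is the first scheduled session after the Week 24 end-of-treatment visit, and that comparison is a natural one to make. The choice should be fixed in writing before outcome data are seen.

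**Working it through.** **Step 1. Is the blank cell real?** The CO row has an entry or a blank for each of the 11 columns. CO is marked at Weeks -1, 0, 1, 4, 12, 24 and 52, which are exactly the in-person sessions. The blood pressure row, also an in-person measure, has the same pattern. Table 3 (Subject Compensation) pays no travel for Week 26, as for the phone sessions at Weeks 8, 14 and 18. The blank is therefore not a table-reading artefact. Scheduled breath samples at Week 26: 0.

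**Step 2. Inputs for size.** The plan states no figure for Week 26, so its Week 24 planning rates are borrowed as an assumption: 33% standard, 47% extended, N = 374, two-sided alpha 0.05, 80% power (Power, Aim 1). Allocation is assumed 1:1, giving 374 / 2 = 187 per arm. The plan gives 187 as a per-site figure, not per arm.

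First, the plan's own figure. With pooled variance and no continuity correction,

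n per arm = [1.96 × √(2 × 0.40 × 0.60) + 0.8416 × √(0.33 × 0.67 + 0.47 × 0.53)]² / 0.14² = (1.358 + 0.577)² / 0.0196 ≈ 191.0, rounded up to 192.

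That is 384 in total against 374 stated. Power at 187 per arm is 79.2% against 80% stated. The plan's figure reproduces closely.

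**Step 3. If the breath-sample rule is carried over to Week 26.** With no samples, abstinence is 0/187 against 0/187. The risk difference is 0 by construction, the odds ratio is 0/0, and Fisher's p = 1. A fitted logistic model is not identified: the treatment standard error is about 36,800, with a perfect-prediction warning.

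**Step 4. If some participants happen to give an unscheduled sample.** Let f be the share who do, equal in both arms and unrelated to abstinence, with everyone else coded as smoking. Observed rates are f × 33% and f × 47%:

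- f = 10%: 3.3% vs 4.7%, power 10%
- f = 50%: 16.5% vs 23.5%, power 39%
- f = 70%: 23.1% vs 32.9%, power 56%

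Partial sampling does not rescue the outcome.

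**Step 5. If self-report is used.** CO matters only for people who report abstinence. Self-reported smokers and people who cannot be reached would be classed as smoking without it. Abstinent classifications:

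- At the Week 24 planning rates: 187 × 0.33 + 187 × 0.47 = 61.7 + 87.9 = 149.6, about 150 of 374 (40%).
- At the plan's Week 52 rates of 28% and 56%: 187 × 0.28 + 187 × 0.56 = 52.4 + 104.7 = 157.1, about 157 (42%).

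All of these would be unverified.

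**The case against.** The strongest reply is that this is a label on one non-primary outcome, and that the documents leave more room than a literal reading suggests. Several parts of it stand.

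- **The no-breath-sample rule.** A reader might infer that the plan itself codes every participant as smoking at Week 26. It does not say so. The rule sits under Abstinence (primary), whose definition names Weeks 24 and 52, and the missing-equals-smoking statement under Accrual is made for primary analyses. Step 3 is what happens if the rule is carried over.
- **The regression.** A reader might infer that the Week 26 comparison cannot be run at all. Aim 1 speaks only of quit rates, and timeline follow-back is scheduled at Week 26, so a self-report comparison is possible. What cannot be produced is the CO-verified version listed under Outcome Assessments.
- **In-person only.** The CO statement says each in-person visit and does not add 'only'. Mid-treatment Assessments lists a CO assessment in a paragraph that covers Week 26. That paragraph also covers phone Weeks 8, 14 and 18 and allows telephone administration, so it does not schedule a Week 26 sample. The note before Table 2 lets in-person sessions move to the telephone and does not describe the reverse.
- **Durability.** A reader might treat Week 26 as the test of whether benefit survives the end of treatment. The CO-confirmed Week 52 primary outcome does that. Weeks 24 and 26 each have a one-week window either way, so both visits can fall around Week 25.

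What does not fall away is the mismatch itself: a CO-verified outcome, no CO test, and no stated alternative.

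**Conclusion.** The point holds as a contained conflict between an outcome definition and the visit schedule. Week 26 point-prevalence abstinence cannot be measured as defined for anyone seen as scheduled. That conclusion rests on the documents alone and does not need the no-breath-sample rule.

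The size depends on which repair the analyst would improvise. Carrying over the primary-outcome rule gives 0% in both arms and no estimable odds ratio. Self-report leaves about 150 of 374 classifications unverified (about 157 at the Week 52 planning rates), assuming 1:1 allocation and planning rates borrowed from other weeks. It would be wrong to say all 374 are unverified, because participants who report smoking need no CO test.

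Nothing here touches the Week 24 and 52 primary outcomes, their power, or Week 12 point prevalence. Prolonged abstinence is defined by self-reported smoking, and continuous abstinence is computed from timeline follow-back, so both survive at Week 26. It should be corrected before analysis, but it is not a threat to the trial's main conclusion.

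**What to change.** Three wording changes:

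1. **Outcome Assessments:** keep CO verification for Week 12 and define Week 26 point prevalence as self-reported 7-day abstinence by timeline follow-back, not CO-verified. Say how participants not reached at Week 26 are coded.
2. **Data Analysis, Aim 1:** state that the Week 26 quit rate is self-reported, and label it unverified in every table.
3. **Abstinence (primary):** state that the CO requirement and the no-breath-sample rule apply at Weeks 12, 24 and 52 by name, regardless of visit mode. They should not be limited to in-person visits: sessions may be moved to the telephone, and a Week 24 or 52 session held that way could then be read as exempt, which would weaken the primary outcome. Naming the weeks keeps such a session counted as smoking. It also makes the rule explicit for Week 12, where the text is now silent.

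No new visit, test or form is needed, since timeline follow-back is already collected at Week 26. The cost is that Week 26 is openly an unverified secondary outcome, not directly comparable with the verified weeks. If the sponsor wants a verified Week 26 rate, the alternative is to schedule an in-person CO test then and amend Tables 2 and 3, at the cost of an extra visit for each participant.

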8. Complete baseline paper and pencil measures to assess 1) background variables that may serve as covariates and will allow for assessment of external validity (e.g., smoking history, demographics); 2) mediators (e.g., affect), 3) moderators (e.g., disease-related information), and 4) baseline smoking behavior.

If eligible at this point, subjects will be scheduled for the first treatment session (Week 0). There must be no more than 60 days between the Intake Session and the first treatment session (Week 0, Pre-Quit). If 60 days elapses between these sessions, all intake measures must be re-administered and evaluated by the study physician before Pre-Quit can occur (both sessions may be completed on the same day pending study physician approval by phone).

Behavioral Counseling (Week 0-Week 18).

All subjects will receive manual-based counseling from a counselor trained and supervised by [name]. The counseling protocol is based on PHS guidelines for smoking cessation treatment (Fiore et al., 2008), used in our past studies with cancer patients ([name] et al., 2010a) and in our ongoing cessation trial at NU (R01 DA025078). Counseling is included given its efficacy at helping smokers quit (Fiore et al., 2008) and to increase study retention. Counseling is provided to both treatment arms through Week 18 to equate for time and attention across arms and since this method was used in varenicline clinical trials (Gonzales et al., 2006) and in our extended therapy trial ([name] et al., 2010b). In-person counseling was selected for most sessions to ensure adequate monitoring of participant safety and adherence throughout the trial. Sessions are arranged at convenient times for the participants, including evenings.

Pre-Quit Session (Week 0): The counseling program begins at Week 0 with a 1-hour in-person "pre-quit" counseling session to prepare for the target quit day. This session focuses on reviewing participant's history and experience with quitting, beliefs about smoking and quitting, and perceived barriers to cessation, and

initiates a quitting plan involving identifying smoking triggers and identifying strategies to increase the chance for success, including relying on social support and altering behaviors associated with smoking. Medication is dispensed at this session and will begin following the session.

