As in our past (Patterson et al., 2009; [name] et al., 2011) and ongoing (U01 DA020830) varenicline trials, a checklist and open-ended questions assess the incidence and severity of varenicline-related side effects at all time-points following the Intake Session. These assessments monitor safety, and dose reductions or suspension of medication may be indicated based on the side effect reporting. Side effects will be a study outcome and a covariate; overall frequency, changes from pre-treatment baseline (Pre-Quit) and the presence of specific side effects will all be tracked. This measure includes potential varenicline-related psychiatric events (Kuehn, 2008) and cardiovascular side effects.

Varenicline Adherence

Medication adherence will be assessed by self-report using a time-line follow-back method and by pill count and collection of used blister packs at each visit as in past varenicline trials (e.g., Gonzales et al., 2006; Jorenby et al., 2006; Ebbert et al., 2009; Niaura et al., 2008). We will also collect blood (10mL) from 50% of participants enrolled at Penn at Week 4 to assess varenicline levels as an adherence measure and to examine the validity of self-report and pill count data. An adherence measure will represent the proportion of total dose taken (adherence = > 80% of dose taken based on self-report, pill-count, and ng/ml for plasma varenicline; Catz et al., 2011).

Integrity of the Blind

Participants may be likely to notice a change in their physiological and/or psychological state that would be best noted following the two-week washout period (Week 14), and their perception may change after they experience the second potential washout period (Week 26). This follows the questions outlined by [name] et al. (2008).

Program Satisfaction

Given the negative perception that many individuals have of Chantix, understanding patient's satisfaction with the program, and how that might change between weeks 12 (standard duration) and 24 (extended duration), will provide a basis for clinical relevance. These questions were modeled after patient satisfaction questionnaires used for a variety of smoking cessation programs.

Outcomes Variables.

Abstinence (primary)

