Staff training will consist of an explanation of the protocol and review of the Case Report Forms. In addition, the duties of each staff person will be outlined and all applicable regulations will be reviewed. Mock sessions with critical feedback will be conducted. The MOP will be used for staff training and to guide procedures throughout the trial. Senior personnel will supervise junior staff and provide re-training in the study protocol as needed.

Monitoring will be conducted in accordance with the University of Pennsylvania Sponsor-Investigator Standard Operating Procedure PM 504. Monitoring days will be conducted periodically throughout the study. The first monitoring day will occur no more than two weeks after the first subject is entered. Subsequent monitoring meetings will be quarterly. The monitoring is conducted by the site IRBs and the PENN Office of Human Research (see www.med.upenn.edu/ohr). Audits are conducted bi-annually or annually and involve the review of regulatory documents, the ascertainment and documentation of informed consent, the compliance with the study protocols, and the completion of CRFs.

Monitoring for Adverse Events (AE) will be conducted in real-time by the study personnel and the on-site Principal Investigators and the study physicians and psychologists. Research staff member will complete side effect assessments and will determine the severity of the adverse events; the relationship of the event to the study drug and the decision on the course of action for the participant will be decided by the site physicians and psychologists after review of the report. Participants will be monitored for the development of adverse events by assessing side effects at each assessment time-point between weeks -1 and 52 as well as through open-ended questions during assessments. Monitoring may increase if required.

Subjects will also be given a 24-hour emergency number they can call if necessary. The PIs and study physicians and psychologists will clinically follow all subjects who are discontinued due to a serious adverse event until it resolves and becomes completely stable, unless a referral to another physician (i.e., specialist) is clinically indicated or requested by the subject. All AEs and SAEs will be documented on an Adverse Events Case Report Form. This information will, in turn, be reported immediately to all necessary regulatory committees, including the FDA.

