- a. Each meeting will consist of 3 parts. First, an open session will occur in which the PI and the DSMB will review the conduct of the trial (e.g., accrual, protocol compliance, general toxicity). Next, to maintain the blind of the study, a closed session involving only the DSMB and the study biostatistician will be held wherein [name] will present unblinded side effect results to the DSMB as requested. This will focus on the presentation of the rate of increase in any side effect from baseline to a follow-up across treatment arms. Lastly, an executive session involving only DSMB members will be held to allow the DSMB the opportunity to discuss the conduct of the trial and outcomes, including toxicities and adverse events, develop recommendations, and take votes as needed.

- b. The DSMB written recommendations will be provided to the PIs and to the IRBs. The DSMB will summarize adverse event reports for the study PI and the IRB Chair, and the PI must implement any DSMB recommendations expeditiously. All DSMB recommendations will also be forwarded to the NIH and the FDA (where necessary).

5. Management of Information for Multi-center Research where a Penn Investigator is the Lead Investigator of a multi-center study, or Penn is the lead site in a multi-site study.

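### Table 2 omits the open-ended side-effect question at Week 0, the visit that the text defines as the pre-treatment baseline and at which it schedules that question (minor)

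*Combined protocol and SAP*

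**What the plan says.** Three places in the protocol set the schedule for side-effect assessment.

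- **Table 2 (Study Measures/Events, Treatment Variables).** The checklist row begins at Week 0: "Side Effects Checklist (SEC) | | X | X | X". The open-ended row begins one column later, at Week 1: "Side Effects (Open-Ended) | | | X | X | X".
- **Treatment Measures, Side Effects.** Here "a checklist and open-ended questions assess the incidence and severity of varenicline-related side effects at all time-points following the Intake Session". Pre-Quit is the first visit after Intake, so this text puts both instruments at Week 0.
- **Data and Safety Monitoring.** Adverse events are to be followed by "assessing side effects at each assessment time-point between weeks -1 and 52 as well as through open-ended questions during assessments". This gives no start for the open-ended questions, and it starts side-effect assessment at Intake, where Table 2 has neither instrument.

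On timing, the Pre-Quit Session paragraph says of Week 0: "Medication is dispensed at this session and will begin following the session".

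On use of the data, the Side Effects paragraph says that "overall frequency, changes from pre-treatment baseline (Pre-Quit) and the presence of specific side effects will all be tracked". For the DSMB closed session, the protocol says that the presentation will focus on "the rate of increase in any side effect from baseline to a follow-up across treatment arms". The Aim 2 analysis compares the arms on how often severe side effects occur and states no adjustment for baseline.

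**The concern.** A change from baseline needs the same instrument before and after the first dose. The checklist has this in both table and text. The open-ended question has it in the text but not in the table.

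The table is likely to decide what happens in clinic. The protocol says that the manual of operations will hold a checklist of measures for each visit, with a case report form for each measure at each week. A form set built from Table 2 would not ask the question at Week 0, and a pre-dose answer cannot be recovered once treatment has begun.

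The population makes this more than a formality. Participants have cancer, and some will probably have symptoms of disease or treatment that a checklist built around varenicline does not list. For these symptoms the open-ended question is the planned side-effect instrument. At stake are two descriptive safety summaries: the change from Pre-Quit and the DSMB's view of increase from baseline.

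**Working it through.** The plan gives no figure on this point to reproduce. The check is a cell count and a comparison of passages.

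**1. Visits per instrument in Table 2**

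| Instrument | Weeks marked | Count |
|---|---|---|
| Checklist | 0, 1, 4, 8, 12, 14, 18, 24, 26, 52 | 10 |
| Open-ended | 1, 4, 8, 12, 14, 18, 24, 26, 52 | 9 |

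The Side Effects paragraph, read literally, gives 10 for both. The difference is 10 − 9 = 1 visit, Week 0.

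**2. Is Week 1 still pre-dose?** No. Medication starts after the Week 0 session. The Week 1 visit falls about 7 days later, and up to 7 + 3 = 10 days later within the window in the note to Table 2. The first open-ended answer is therefore given on treatment.

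**3. What this does to a change from baseline.** Take a symptom that only the open-ended question picks up, and let p0 be its true prevalence at Week 0 and pt its prevalence at a later visit.

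- Intended summary: pt − p0.
- Under Table 2, p0 is not observed, so the summary cannot be computed.
- If such reports are dropped, the tables cover checklist items only.
- If the missing value is read as absence, the summary becomes pt − 0 = pt, too high by p0. A symptom with stable prevalence and no drug effect then shows an increase of p0 where the true increase is 0.

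No section says which handling applies. The documents give neither p0 nor the contents of the checklist, so the excess cannot be put into numbers from them.

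**4. What it does to the comparison of arms.** Randomisation makes p0 equal in expectation in the two arms, and both receive the same active drug until Day 85. With missing read as absence, the difference between arms is (pt,ext − 0) − (pt,std − 0) = pt,ext − pt,std. This equals the intended difference in expectation, because p0 cancels. Absolute rates rise about equally in both arms, and a ratio of rates would be pulled towards 1.

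**5. Which summaries are affected.** Of the three summaries in the Side Effects paragraph, only the change from Pre-Quit needs a Week 0 value. Overall frequency and presence of specific effects do not. The DSMB's increase from baseline does need one.

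**The case against.** The strongest reply is that the text already schedules the question at Week 0, so this is a one-cell slip in a table. That stands as a description of the defect: the documents contradict each other, and they do not show a settled decision to go without a baseline. It does not remove the need to reconcile them before forms are built.

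A second reply is that a pre-existing symptom could be recognised by other means. A medical history, physical examination and medication review take place at Intake. Depression and anxiety, cognitive function, quality of life and concomitant medication are recorded at Week 0. Clinicians judge whether an event is related to study drug. This stands in part. These sources can help to identify an old symptom, but none is a matched pre-dose answer to the same question. The medical history is described as a review for contraindications, and up to 60 days may separate Intake from Week 0. The DSMB summary is not limited to drug-related events.

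A reader might also infer two stronger claims, and the documents support neither.

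- *Every pre-existing symptom off the checklist is necessarily counted as new.* This needs a rule that a missing Week 0 value means absence, and no such rule is stated.
- *The gap damages the Aim 2 test of severe side effects.* That analysis states no baseline subtraction, so severe background symptoms would enter it with or without a Week 0 question. The 95% and 88% used to plan it come from an earlier bupropion trial in cancer patients, so they may already include background of this kind. Subtracting a further assumed share from those rates would risk counting it twice.

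**Conclusion.** The contradiction between Table 2 and the Side Effects paragraph is real. It concerns one visit, and that visit is the defined baseline. If Table 2 is followed, the change-from-Pre-Quit and DSMB increase-from-baseline summaries cannot be computed for symptoms reported only in answer to the open-ended question. Such symptoms would be dropped or counted as new. Counting them as new would overstate absolute rates by their baseline prevalence, a quantity the documents do not give, and would do so about equally in both arms.

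The conclusion assumes that sites work from Table 2 and that some symptoms are not on the checklist. It does not extend to the abstinence outcomes or to the Aim 2 comparison of severe side effects. Rating: minor, but worth correcting because a lost baseline cannot be recovered.

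**What to change.** 1. In Table 2, mark the open-ended side-effect question at Week 0, to be asked before the first dose, so that the table agrees with the Side Effects paragraph. Align the start week given under Data and Safety Monitoring at the same time.
2. In the change-from-baseline and DSMB tables, count an open-ended report as treatment-emergent only if it is new, or worse in severity, compared with Pre-Quit.
3. For any participant without a Week 0 open-ended record, limit those tables to checklist items, and say so in a footnote.

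The cost is a few minutes at a visit that already takes place in person, one table cell, and a sentence or two in the analysis and DSMB sections. The sample size and the Aim 2 test are unchanged.
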